Therefore, in order to investigate the impact of face coverings on exercise capacity, research will take place in two phases:

Phase I: Participants will be randomized and complete 2 treadmill trials including (1) cardiopulmonary exercise tests (CPET) with face covering, and (2) CPET without face covering.

Phase II: Participants will be randomized and will complete 2 cycle ergometer trials including (1) cardiopulmonary exercise tests (CPET) with face covering, and (2) CPET without face covering. Cognitive testing will occur incrementally as exertion increases.

SPECIFIC AIMS & OUTCOMES

Phase I:

The proposed study consists of 4 specific aims:

Specific Aim 1: Describe the primary and secondary outcomes of athletes during a Cardiopulmonary Exercise Test (CPET) on a treadmill with (arm 1) and without (arm 2) the use of a face covering.

Specific Aim 2: Conduct a randomized crossover trial to determine if there is a significant difference in maximal and submaximal aerobic exercise capacity (VO₂ max; assessed during the CPET) in athletes with (arm 1) and without (arm 2) the use of a face covering.

Specific Aim 3: Describe participants' experiences' while wearing a face covering during exercise.

Specific Aim 4: Determine reliability of the Attitudes Toward Face Coverings Questionnaire

Primary Outcomes:

- VO₂ max during treadmill Cardiopulmonary Exercise Testing (CPET)
- Test duration (time) on a CPET

Secondary Outcomes

- Minute ventilation (VE) at max during CPET

- Subjective dyspnea rating (Borg) at max during CPET
- Subjective exertion rating (Borg) at max during CPET
- O₂ saturation at baseline, each stage, and recovery during CPET
- Blood pressure at baseline, each stage, and recovery during CPET
- Max heart rate during CPET
- Respiratory quotient at max during CPET
- Attitudes Toward Face Coverings Questionnaire
- Scale of Measuring Subjective Perceptions Questionnaire

Phase II:

Specific Aim 1: Describe the primary and secondary outcomes of participants during a Cardiopulmonary Exercise Test (CPET) on a cycle ergometer with (arm 1) and without (arm 2) the use of a face covering.

Specific Aim 2: Conduct a randomized crossover trial to determine if there is a significant differences in cognitive performance outcomes in participants with (arm 1) and without (arm 2) the use of a face covering. Cognitive performance will be measured by simple reaction time and accuracy on the SRT task.

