Presence of beards	Beards interfere with the fit of the Vo2 mask. Therefore, participants with beards will be asked to shave prior to their visit. If they are unwilling to shave, they will not be eligible for the study.
Claustrophobia	Participants who have been diagnosed or treated for claustrophobia will be excluded. Claustrophobia is a contraindication of the CPET test.
Currently experiencing symptoms of COVID-19 or < 7 days since last symptoms	Participants will be screened for COVID-19 symptoms using the BSW COVID-19 screener; if participants have past history of COVID-19 based on laboratory testing, participants will be ineligible if <7 number of days since last symptoms

Study Procedures

Phase I & II Subject Recruitment

Up to 100 participants (50 for each phase) will be recruited from Baylor Scott & White Sports Therapy and Research at The Star in Frisco, Texas through approved fliers, calls, emails, and social media, as well as through local community organizations, healthcare clinics, and collaborating centers and organizations, including but not limited to the Sports Academy and the University of North Texas. IRB-approved fliers will be posted at BSW The Star and at affiliated organizations and collaborators in the DFW Metroplex and surrounding areas. In addition, members of the study team will attend meetings with local clinicians and community partners to inform them of the purpose of the study. The study flier will contain information on the study and methods to contact the study team including (1) a QR code linked to the eligibility screener which will be stored in a REDcap, a HIPAA-compliant (21 CFR Part 11) secure web application, (2) a phone number, and (3) an email address of the study coordinator. Interested individuals may contact the study team by phone or email to learn more about the study and undergo a telephone screener or follow the QR code to complete the eligibility screener electronically. A snowball sampling technique will be used for further recruitment whereby interested participants will be invited to ask other athletes they know to contact the study team about participation. Eligible individuals will be contacted by a member of the study team to schedule their first study visit. It is anticipated that recruitment will take 2-4 weeks during each phase to achieve our desired sample size.

Subject Information and Screening

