The CPET will be performed in an area with immediate access to an automated external defibrillator (AED). Resting blood pressure, heart rate, pulse oxygenation and will be measured and recorded. Explanation of the Borg dyspnea and exertion scales will occur by an Exercise Physiologist prior to beginning test. Each subject will be asked to perform the exercise test to the best of their abilities. At the beginning of the test, subjects will be instructed to perform a walking warm up of 3 minutes at 1.7 speed and 0% incline.

- The Borg Rating of Perceived Exertion (6-20) scale will be used during the test to assess subjective exertion
- The Modified Borg Dyspnea Scale (0-10) will be used to assess subjective shortness of breath.
- Intermittent blood pressure measurements and pulse oximeter measurements will be taken by an exercise physiologist and heart rate will be monitored constantly.

Testing will be terminated if any of the following occurs: (a) subject becomes symptomatic; (b) pain is reported; (c) subject wishes to terminate test; (d) unsafe drop in blood pressure or hypertension over 250/120 mmHg reported; or (e) subject reports a “20” on Borg RPE scale or “10” on Dyspnea scale. Other termination of the test is reserved for the clinical judgment of research staff to ensure safety of the subject. After termination

of the test, subject will be instructed to perform a walking cool-down of 3 to 5 minutes. After subject has completed cool-down, recovery blood pressure, heart rate and pulse oxygenation will be measured and recorded. After completion of the first test, subject will be scheduled for second CPET 7-10 days later to allow for adequate recovery. When data collection is complete, CPET data will be gathered from metabolic cart and matched with subject testing materials.

Phase II CPET Procedures:

Among individuals with history of COVID-19, an ECG will be performed prior to CPET procedures and will be monitored throughout the CPET.

The CPET will be performed in an area with immediate access to an automated external defibrillator (AED). Resting ECG (among individuals with history of COVID-19), blood pressure, heart rate, pulse oxygenation, and blood lactate will be measured and recorded. Explanation of the Borg dyspnea and exertion scales will occur by an Exercise Physiologist prior to beginning test. Each subject will be asked to perform the exercise test to the best of their abilities.

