All equipment will be disinfected between each subject contact using BSWH approved disinfectant wipes (sani cloths AF3) using Cidezyme and Cidex OPA with testing strips as per factory requirements. This process will take place in a designated “dirty room” to perform high level disinfecting (e.g., sink and proper ventilation) and has been approved by BSWH Infection Prevention and is effective against COVID-19 spread in addition to other high-consequence infectious diseases (procedure provided in supplementary procedures).

Data Collection Details

All data will be collected during each study visit on paper case report forms or via direct data entry in the study's REDCap database. Complete paper case report forms will be entered in the REDCap database within 3 days of collection. Sources for data include patient reported data and objective results from CPET evaluation.

Staff Training

All study staff will be trained on study procedures at the project launch meeting and subsequent support meetings.

Venue

In-person sessions will take place at BSW Sports Therapy and Research at The Star in Frisco, Texas.

Communication

To facilitate appointment scheduling and timely ongoing communication between study staff and participants, study staff will communicate with participants via their preferred methods of communication (established during screening), whether phone, email, or text message. All communication will be documented on communication logs that will be kept in patient files or in electronic communication logs stored in Excel. Participants will be asked not to transmit sensitive health information via text message, but will be given a secure email message that they can reply to when communicating sensitive health information digitally. Participants will be informed that they may be responsible for charges incurred by text messages.

Study Testing Visits

Participants will be asked to come in at two time points for measurements, surveys, and testing.

Schedule of Assessments**Phase I:**

Study Visit	Visit Details

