Initial visit/Visit 1	
 • COVID-19 screening and temperature check is performed • Demographic information (age, race, ethnicity, sex, income, insurance, work history, sport) • Clinical and physical activity information (Physical activity readiness questionnaire, physical activity history, tobacco use, marijuana use, vaping, history of asthma, height, weight, use of beta-blockers) • Attitudes Towards Face Coverings Questionnaire • Cardiopulmonary exercise testing (CPET) 
 ◦ Dyspnea scores ◦ Exertion scores ◦ Pulse ox measurements ◦ Blood pressure measurements • Scale of Measuring Subjective Perceptions • Participant will be scheduled for 2nd CPET
Visit 2	
 • COVID-19 screening and temperature check is performed • Attitudes Towards Face Coverings Questionnaire • Cardiopulmonary exercise testing (CPET) 
 ◦ Dyspnea scores ◦ Exertion scores ◦ Pulse ox measurements ◦ Blood pressure measurements • If subject is randomized to face covering: Qualitative question describing experience • Quantitative and qualitative questions about difficulty of wearing face coverings during CPET and differences completing the CPET with and without a face covering. • Scale of Measuring Subjective Perceptions

Phase II:

Study Visit	Visit Details
Initial visit/Visit 1	
 COVID-19 screening and temperature check is performed Demographic information (age, race, ethnicity, sex, income, insurance, work history, sport) If subject reports a previous COVID-19 diagnosis: information regarding symptoms, severity, hospitalization, health changes, experience while exercising, and vaccinations will be collected. Clinical and physical activity information (Physical activity readiness questionnaire, physical activity history, tobacco use, marijuana use, vaping, history of asthma, height, weight, use of beta-blockers) Attitudes Towards Face Coverings Questionnaire ECG among individuals with history of COVID-19 Cardiopulmonary exercise testing (CPET) 
 Heart rate Dyspnea scores Exertion scores Pulse oximetry measurements Blood pressure measurements Lactate measurements (pre and post-CPET) Scale of Measuring Subjective Perceptions Participant will be scheduled for 2nd CPET

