Subject IDs will be recorded on all pages of case report forms. Protected health information will not be used during data analysis or dissemination. Subjects will only be referred to by their unique Subject IDs.

Data Entry in Database

All subject tracking information will be maintained in a password-protected Excel spreadsheet and REDcap, a HIPAA-compliant (21 CFR Part 11) secure web application on a BSWH computer by trained study staff.

All case report forms and outcomes data will be input into REDcap, a HIPAA-compliant (21 CFR Part 11) secure web application on a BSWH computer by trained study staff.

Data Quality Assurance

Data management functions will occur on a monthly basis and will include data quality checks and verification, as well as internal edit and logic checks (e.g., out of range values, internal inconsistencies). Ten percent of charts will be audited for source document and data entry review. Cross tabulation checks using SAS will also be used. Data will be stored and backed-up periodically on the biostatistician's space on the secure server. Descriptive statistics will be calculated and included into quarterly reports to ensure the quality of data and progress of the study.

Record Retention

All paper source documents will be kept in a double locked storage cabinet in the BSW research office at The Star. All electronic data will be kept on a secure server per federal guidelines. All data will be maintained for two years after study termination per federal guidelines and will be disposed of in accordance to current BSWRI policy.

Management of Subject Safety/ Adverse events

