Participant characteristics will be summarized with means and standard deviations or medians and interquartile ranges for numerical variables, and counts and percentages for categorical variables. The primary outcomes, VO₂ max and test duration, will first be assessed for normality using a Kolmogorov-Smirnov test prior to determining the analysis to be used. If the distribution meets the normality assumption, paired t-tests will be used to determine if there is a difference between participants when wearing and not wearing a face covering. If the distribution does not meet the normality assumption, Wilcoxon signed-rank tests will be used. All secondary outcomes will follow the same analysis plan of assessing the normal distribution assumption to determine the appropriate test for each outcome. Inter-rater reliability analysis will be conducted for the Attitudes for Face Coverings Questionnaire. All analysis will be performed using SAS 9.4 at a 0.05 significance level.

Risks & Benefits

- Physical risks: The potential risks include any and all risks associated with exercise including muscular injury, increased blood pressure and heart rate, and cardiac arrest. Other risks include hypoglycemia post-exercise and lightheadedness or syncope. Although some risks are unavoidable, the careful monitoring of signs and symptoms by the subject and clinical staff will minimize these risks.
- No psychological risks have been identified by participating in this study.
- No social risks have been identified by participating in this study.
- No economic risks have been identified by participating in this study.
- No legal risks have been identified by participating in this study.
- Potential benefits: Participants in this study may experience greater confidence in performing aerobic activities and may gain a better understanding of their personal functional exercise capacity at the time of testing. Participants may also better understand their body's response to exercise with and without a face covering which may impact training and performance in recreational and occupational ventures.

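### Phase I Aim 4 needs the questionnaire's reliability, but the only analysis named is inter-rater, which the described data cannot supply; the two visits do support test-retest reliability

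*Combined protocol and SAP*

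**What the plan says.** Phase I Specific Aim 4 (Specific Aims & Outcomes) is to "Determine reliability of the Attitudes Toward Face Coverings Questionnaire". It does not say which kind of reliability. The Data Analysis section contains the only matching analysis: "Inter-rater reliability analysis will be conducted for the Attitudes for Face Coverings Questionnaire". It names no coefficient, no set of completions and no raters.

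On data collection:

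- The Phase I Schedule of Assessments lists the "Attitudes Towards Face Coverings Questionnaire" once at Visit 1 and once at Visit 2, each time above the cardiopulmonary exercise test (CPET).
- Study Testing Visits confirms the number of occasions: "Participants will be asked to come in at two time points for measurements, surveys, and testing".
- Phase I CPET Procedures gives the spacing: "After completion of the first test, subject will be scheduled for second CPET 7-10 days later to allow for adequate recovery".
- Data Collection Details states: "Sources for data include patient reported data and objective results from CPET evaluation". It mentions no observer rating.
- Phase I & II Subject Recruitment gives the size: "Up to 100 participants (50 for each phase) will be recruited".

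The questionnaire's name varies slightly between sections; I take it to be one form.

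**The concern.** Inter-rater reliability measures how far different raters agree about the same subject. It has meaning only if each subject is scored by two or more people. An attitudes form that each participant answers once per visit has no second rater.

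The stated analysis for Aim 4 therefore does not match the data the schedule produces. If this stands, the type of reliability and the coefficient will have to be chosen later, possibly with the responses in view. The form is also a Phase I secondary outcome, so its reliability bears on how that result is read.

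**Working it through.** The plan gives no reliability target, coefficient or precision, so there is no figure to reproduce. The check has a structural part and an illustrative part.

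**1. Can the named quantity be estimated?** For n subjects with k scores each, the within-subject degrees of freedom are n(k − 1), with n = 50 in Phase I.

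- Inter-rater: k is the number of raters per person per occasion. The documents describe one score, so 50 × (1 − 1) = 0. Rater disagreement cannot be estimated.
- Test-retest: k is the number of occasions, which is two. 50 × (2 − 1) = 50, so it can be estimated.

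**2. Is a second rater described elsewhere?** The nearest text is in Data Quality Assurance: "Ten percent of charts will be audited for source document and data entry review". That compares records with their source; it does not re-score attitudes.

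**3. How precise would test-retest be?** The ICC values here are assumptions. For two occasions, F = (1 + ICC)/(1 − ICC). Divide and multiply F by q, the 97.5% point of the F distribution on (n − 1, n − 1) degrees of freedom, then convert each limit back with (F − 1)/(F + 1). At n = 50 and ICC 0.80: F = 1.80/0.20 = 9.0 and q = 1.762. The limits for F are 5.107 and 15.86, giving 4.107/6.107 = 0.67 and 14.86/16.86 = 0.88.

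| Completing both visits | Assumed ICC | 95% CI |
|---|---|---|
| 50 | 0.70 | 0.53–0.82 |
| 50 | 0.80 | 0.67–0.88 |
| 50 | 0.90 | 0.83–0.94 |
| 40 (assumed) | 0.80 | 0.65–0.89 |

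**4. What if attitudes really change between visits?** If the form is completed before the CPET, as the list order suggests, a maximal test falls between the two completions. Under 1:1 randomization about half the participants do that test masked. Suppose the mask-first half shifts by d standard deviations (SD) and the other half does not shift. With a true ICC of 0.80 and d = 0.5:

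- Absolute agreement: 0.80/(1 + d²/4) = 0.80/1.0625 = 0.753.
- Consistency: 0.80/(1 + d²/8) = 0.80/1.03125 = 0.776.

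**5. Would the proposed report show such a shift?** With score variance 1, the SD of Visit 2 minus Visit 1 is √(2(1 − ICC)) = √0.40 = 0.632 at ICC 0.80. The 95% CI half-width for the mean difference is t × 0.632/√n:

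- All 50: 2.010 × 0.632/√50 = 0.18 SD.
- One sequence of 25: 2.064 × 0.632/√25 = 0.26 SD.

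With a 0.5 SD shift in 25 mask-first participants, a one-sample t test of the difference at the two-sided 5% level has power of about 97% at ICC 0.80 and 87% at ICC 0.70 (noncentral t). Comparing the two sequences' ICCs instead would flag the same shift in only about 10% of simulated trials (20,000 runs, ICC 0.80). The mean difference by sequence is therefore the useful companion to the ICC.

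**The case against.** The strongest reply is that the aim says only reliability, and that the inter-rater sentence may be a slip for test-retest. Even so, the text names the wrong type and no coefficient, so it still needs correcting.

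Other points have some force:

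- **Self-completion is inferred.** No section says who completes or scores the form, and the form is not shown. The accurate statement is that the data as described do not support an inter-rater coefficient. The fix allows for raters if they exist.
- **Test-retest is not the only option.** If the form has several items, internal consistency could be estimated from one completion, with no exercise test in between. This stands as a possible addition. It neither rescues the inter-rater sentence nor measures stability over time.
- **The form has two roles.** As a secondary outcome it falls under the paired comparisons in Data Analysis. The same two completions would then be tested for a difference and treated as stable replicates. This stands, and the report needs to separate real change from unreliability.
- **Absolute agreement is a choice.** It is the index more affected by a real shift (0.753 against 0.776 above). The intervals in the table are also of the consistency type. They match absolute agreement when there is no shift; with a 0.5 SD shift in the mask-first half, the simulated 95% range of the absolute-agreement estimate is about 0.61–0.85.

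None of these makes the stated analysis feasible.

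**Conclusion.** The concern holds. The inter-rater analysis named for Phase I Aim 4 cannot be estimated from the data described: one score per participant per visit leaves nothing from which to measure disagreement between raters. Test-retest reliability can be estimated with useful, though not tight, precision.

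The structural conclusion rests on there being no undescribed second rater. The precision and shift figures rest on assumed ICCs, shifts and completion numbers, none of which the documents give. The matter should be corrected, but its reach is limited to Aim 4. VO₂ max, test duration and the mask comparison do not depend on it.

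**What to change.** Replace the sentence in Data Analysis with wording such as:

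> Test-retest reliability of the questionnaire between Visits 1 and 2 will be estimated in Phase I participants with a two-way, absolute-agreement, single-measure ICC and 95% CI (quadratic-weighted kappa for any single ordinal item), together with the Visit 2 minus Visit 1 mean difference and 95% CI, overall and by randomized sequence.

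Also state whether the form is completed before or after the CPET, and how the reliability analysis relates to the form's use as a secondary outcome. If the form has several items, internal consistency at Visit 1 could be added. If raters do score the form, describe them and the duplicate scoring instead, and keep the inter-rater analysis with a named coefficient.

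The cost is a sentence or two of analysis text and a note on timing, with no new data, visits or participants. The downside is that absolute agreement counts any real change between visits as disagreement; the mean difference by sequence lets readers see when that has happened.
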